4.3 End of study

The study will end when the proper number of the follow-up questionnaires will be reached according with the sample size (see paragraph 9.2).

5. STUDY ENDPOINTS

In order to setup the questionnaires for primary and secondary endpoints, a systematic review of the literature has been performed using the following key words “Breast cancer and decision aid”. At the end of the process accomplished by two independent reviewers, a total of 9 trials has been included. The comparative analysis of the tools used in the trials has been presented and discussed with partners and scientific committee, allowing to identify areas and items to consider within the questionnaires of the study (described below).

5.1 Primary endpoints

Informed choice will be measured according to the three-dimensional framework of Marteau et al. (26), which covers knowledge, attitude and intention. The statistical hypothesis for the primary

endpoint is of superiority, the study is designed to detect a 10% difference between the control and the intervention group, according to the literature available (22, 27).

Knowledge will be measured using a questionnaire developed on the basis of literature (22, 27). It will be structured in thirteen questions with multiple choice answers, with two to three options. Ten questions will be qualitative and 3 will be numerical. The score and threshold to reach an “adequate knowledge” were decided *a priori*, following the approach described in the literature (22, 27). Each correct answer will receive one point. The maximum total score is 13 out of 13. A score of 8 out of 13 (about 60%) or higher would be considered “adequate knowledge”.

Attitude will be measured through a scale used in the literature available (22, 27), consisting of six items with five response options from 1 to 5, with a total score from 6 to 30. For informed choice, we set the threshold for a positive attitude at 24 and consequently the score <24 point a negative attitude.

Intention to be screened will be measured using one item with five responses: Definitely will, Likely to, Unsure, Not likely to, Definitely will not. For informed choice, we classified “definitely will” and “likely to” as positive intentions. This item will be collected at the end of the information session on the web and in the follow-up questionnaire. In case of no consistency between the two answers, the answer in the follow-up questionnaire will be considered as conclusive.

The informed choice will be assessed as a dichotomous outcome. A woman will be considered as able to express an informed choice if she has adequate knowledge and her attitudes and intentions are consistent (both positive or both negative) in the follow-up questionnaire.

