Inclusion criteria	
 • Women aged 45-69, according to the target age of the screening centres involved; • New invited women in mammography screening programme.
Exclusion criteria	None
Assessment schedule	Baseline questionnaire prior to randomization Follow-up questionnaire 7-10 days after the randomization
Endpoints	
Primary
 
Informed choice, based on the available literature, will be measured according to the three-dimensional framework which covers knowledge, attitude and intention. Knowledge will be measured using a questionnaire structured in thirteen questions with multiple choice answers, with two to four options. Ten questions will be qualitative and 3 will be numerical. A score of 8 out of 13 (about 60%) or higher would be considered “adequate knowledge”.
 
Attitude will be measured through a scale consisting of six items with five response options from 1 to 5, with a total score from 6 to 30. For informed choice, we set the threshold for a positive attitude at 24 and consequently the score <24 point a negative attitude.
 
Intention to be screened will be measured using one item with five responses: Definitely will, Likely to, Unsure, Not likely to, Definitely will not. For informed choice, we classified “definitely will” and “likely to” as positive intentions.
 
A woman will be judged to have made an informed choice if she has adequate knowledge and her attitudes and intentions are consistent (both positive or both negative) in the follow-up questionnaire.

Secondary	
Participation rate to the breast cancer screening programme will be assessed as a percentage of women who actually participate, both in intervention and in the control group.
 
Satisfaction with the given information will be measured using 8 items with three points scale.
 
The time spent on the pages on the web decision aid and in the web brochure will be assessed through Pickwick software. Only for the web decision aid, through the same software, the number of pages visited, the frequency of access and level of detail reached will be calculated.
 
Decisional conflict will be assessed using the validated and widely used Decisional Conflict Scale-SURE version, consisted in four-item scale.

Planned study period	15 months (september 2017-december 2018)

LIST OF ABBREVIATIONS AND DEFINITION OF TERMS

e-CRF	Electronic Case Report Form

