In the organized mammography screening program, the presence of two expert radiologists increases the ability to identify a breast tumor

- True
- False

The usefulness of an organized mammography screening program is:

- Totally recognized by doctors and researchers
- Questioned by some doctors and researchers

For the next few questions, I would like you to imagine 1000 ordinary women who are 50 years old who have participated regularly in organized mammography screening program for 30 years

How many women do you think will avoid dying from breast cancer because of screening?

- 8
- 50
- 150

How many women do you think will be diagnosed and treated for a breast cancer that is not harmful?

- 4
- 25
- 70

Now, I would like you to imagine 1000 ordinary women who are 50 years old who have not participated in organized mammography screening program, in their next 30 years.... How many die of breast cancer?

- 20
- 80
- 140

ATTITUDE

For you, having breast screening is.....

A bad thing	Not a bad thing
1 2 3 4 5	
Beneficial	Not beneficial
1 2 3 4 5	
Harmful	Not harmful
1 2 3 4 5	
A good thing	Not a good thing
1 2 3 4 5	
Worthwhile	Not worthwhile
1 2 3 4 5	
Important	Unimportant
1 2 3 4 5	

INTENTION

Intending to be screened

Definitely will	Likely to	Unsure	Not likely to	Definitely will not
-----------------	-----------	--------	---------------	---------------------

FOLLOW-UP QUESTIONNAIRE

ATTITUDE

For you, having breast screening is.....

A bad thing

Not a bad thing

1 2 3 4 5

Beneficial

Not beneficial

1 2 3 4 5

Harmful

Not harmful

1 2 3 4 5

A good thing

Not a good thing

1 2 3 4 5

Worthwhile

Not worthwhile

1 2 3 4 5

Important

Unimportant

1 2 3 4 5

SATISFACTION/ACCEPTABILITY OF THE INFORMATION

Thinking back to the type of information material you have read ...			
Was there enough information?	Too much	Too little	Fair
Was the information on benefit new to you?	All or almost all	Some	None
Was the information on harm new to	All or almost all	Some	None

you?			
Was the information clear?	All or almost all	Some	None
The information seemed...	In favor of screening	Balanced	Against screening
Did it help you to decide?	Yes	Not much	No
Would you recommend it to other women?	Yes	Not much	No
Only for Decision-Aid	All or almost all	Some	None
Was the controversy new to you?			

DECISIONAL CONFLICT (SURE QUESTIONNAIRE)

Sure of myself

Do you feel SURE about the best choice for you?

Yes
 No

Understanding information

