Do you know the benefits and risks of each option?

Yes
 No

Risk-benefit ratio

Are you clear about which benefits and risks matter most to you?

Yes
 No

Encouragement

Do you have enough support and advice to make a choice?

Yes
 No

INTENTION

Intending to be screened

Definitely will	Likely to	Unsure	Not likely to	Definitely will not
-----------------	-----------	--------	---------------	---------------------

KNOWLEDGE

What is a SCREENING mammogram?

- A mammogram you have when you're healthy
- A mammogram you have if you notice a change or lump in your breast

An organized mammography screening program can detect a breast cancer in an early stage and lead to less invasive surgery and treatment

- True
- False

Which of the following statements about mammography reflects your opinion?

Regular mammography every two years in women who are well:

- Prevents the risk of breast cancer
- Does not prevent the risk of breast cancer

Who do you think is more likely to die from breast cancer?

- Women who have screening mammograms
- Women who do not have screening mammograms

Do you think a screening mammogram will find every breast cancer?

- Yes
- No

Do all women with an abnormal screening mammogram result have breast cancer?

- Yes
- No

Which of these 2 statements best describes over-detection?

- Screening finds a cancer that would never have caused trouble
- Screening finds an abnormality but extra tests show it is not cancer

Screening leads some women with a harmless cancer to get treatment they do not need.

- True
- False

In the organized mammography screening program, the presence of two expert radiologists increases the ability to identify a breast tumor

- True
- False

The usefulness of an organized mammography screening program is:

- Totally recognized by doctors and researchers
- Questioned by some doctors and researchers

For the next few questions, I would like you to imagine 1000 ordinary women who are 50 years old who have participated regularly in organized mammography screening program for 30 years

How many women do you think will avoid dying from breast cancer because of screening?

- 8
- 50
- 150

How many women do you think will be diagnosed and treated for a breast cancer that is not harmful?

- 4
- 25

70

Now, I would like you to imagine 1000 ordinary women who are 50 years old who have not participated in organized mammography screening program, in their next 30 years.... How many die of breast cancer?

20

80

140

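### As printed, the knowledge answer key gives itself away: the first option is right on 8 of 13 items, which is exactly the pass mark, and the lowest number is right on all three numerical items

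*Combined protocol and SAP*

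**What the plan says.** Section 5.1 describes a knowledge test of "thirteen questions with multiple choice answers, with two to three options". It adds: "Ten questions will be qualitative and 3 will be numerical". Scoring is simple: "Each correct answer will receive one point". The pass mark follows: "A score of 8 out of 13 (about 60%) or higher would be considered" adequate knowledge, said to be fixed in advance in line with the literature. A woman counts as making an informed choice if "she has adequate knowledge and her attitudes and intentions are consistent (both positive or both negative) in the follow-up questionnaire".

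The synopsis differs slightly, with "thirteen questions with multiple choice answers, with two to four options". Appendix 3 (Section 14.3) agrees with Section 5.1: ten items have two options and three have three. No item offers a 'don't know' answer. The same items appear in the same printed order at baseline and at follow-up. The numerical items include "How many women do you think will avoid dying from breast cancer because of screening" (8, 50, 150) and "How many women do you think will be diagnosed and treated for a breast cancer that is not harmful" (4, 25, 70); the third asks for deaths without screening (20, 80, 140).

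The plan describes no correction for guessing and no randomisation of option order, and it does not set the pass mark against the chance level of this item set.

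**The concern.** Adequate knowledge is a necessary part of the primary endpoint. With forced choice among two or three options, a woman who does not know an answer still has a good chance of a point. An answer key that is uneven by position, and always lowest in the numerical items, adds a cue that has nothing to do with knowledge.

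The cue matters most for items 12 and 13 (women overdiagnosed per 1000, and deaths per 1000 without screening). The decision aid states both figures; the brochure states neither. These items should separate the arms, yet a control woman can get both right by taking the first or smallest number.

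**Working it through.** **The plan's own figure.** 8/13 = 61.5%, which agrees with the stated 60% or so.

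**Answer key.** No key is printed. It can be inferred without ambiguity from the brochure (Section 14.1) and the decision aid (Section 14.2).

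| Item | Topic | Correct option as printed |
|---|---|---|
| 1 | Meaning of a screening mammogram | first |
| 2 | Early stage, less invasive treatment | first |
| 3 | Prevents breast cancer or not | second |
| 4 | Who is more likely to die | second |
| 5 | Finds every cancer | second |
| 6 | Abnormal result means cancer | second |
| 7 | Meaning of over-detection | first |
| 8 | Unneeded treatment | first |
| 9 | Two radiologists | first |
| 10 | Usefulness recognised or questioned | second |
| 11 | Deaths avoided: 8 | first, lowest |
| 12 | Overdiagnosed: 4 | first, lowest |
| 13 | Deaths without screening: 20 | first, lowest |

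First option correct: items 1, 2, 7, 8, 9, 11, 12, 13 = 8 of 13, equal to the cut-off.

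**Pure guessing.** Score X = Bin(10, 1/2) + Bin(3, 1/3).

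- Mean = 10/2 + 3/3 = 6.0. Variance = 10/4 + 3 × 2/9 = 3.17, so the SD is 1.78.
- The numerical part is 0, 1, 2 or 3 with probabilities 8/27, 12/27, 6/27, 1/27. The matching tails of Bin(10, 1/2), at ≥8, ≥7, ≥6 and ≥5, are 56, 176, 386 and 638 out of 1024.
- P(X ≥ 8) = (8×56 + 12×176 + 6×386 + 1×638) / (27×1024) = 5514/27648 = 19.9%.
- If the numerical items had four options, as the synopsis would allow: (27×56 + 27×176 + 9×386 + 638) / (64×1024) = 15.8%.

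**Lowest number always, other ten guessed.** Three points are certain, so five of ten are needed: 638/1024 = 62.3%.

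**Partial knowledge.** With k qualitative items known and the rest guessed, the pass probability is 38% (k = 2), 50% (k = 3), 63% (k = 4), 76% (k = 5) and 96% (k = 7).

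**Effect on the difference between arms.** Let p be the true proportion with adequate knowledge in an arm, and f the pass probability of women without it. The scored proportion is p + f(1 − p), so a true difference d is seen as (1 − f)d. With f = 0.199, the assumption being that every such woman knows nothing and guesses at random, the difference keeps 80% of its size: 10 points become 8.0. The loss of one fifth belongs to that assumption.

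**First option throughout the follow-up questionnaire.** The attitude items alternate in direction. Scored so that a high total is favourable (items 2, 4, 5 and 6 reversed), all first options give 1 + 5 + 1 + 5 + 5 + 5 = 22. Without reversal they give 6. Both are below 24, so attitude is negative. The first intention option is the most positive one. Attitude and intention disagree, and she is not counted as an informed choice.

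**The case against.** The items came from a review of nine trials (Section 5), the threshold was set in advance, and the Italian version was tried in a small group (Section 5.3). That trial looked at clarity, understandability and length, not at how well the score discriminates, so it does not answer the point. Several other replies do stand.

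- **Straight-lining.** A reader might infer that a woman ticking first options enters the endpoint as informed. She does not: the attitude and intention condition excludes her if she does so throughout the questionnaire.
- **Equal guessing in both arms.** A reader might infer that any share of guessers dilutes the effect. If the share is the same in both arms, it raises both rates equally and leaves the absolute difference alone. Dilution needs more uninformed women in the control arm.
- **Power.** Putting 50% and 60% through the guessing model gives 60.0% and 68.0%, and power at 408 per arm falls from 82% to 66% (test without continuity correction). That loss is not established. Section 9.1.3 gives its planning rates for informed choice and nowhere says that they are free of guessing; if they came from similarly scored instruments, guessing is already in them. The sum also ignores the attitude and intention condition.
- **Discrimination.** The 19.9% is for a woman with no knowledge, and both arms read relevant material before follow-up. A rise from 20% to 76% with five items known and 96% with seven is a real gradient, so the test is not uninformative.
- **Display order.** The documents neither confirm nor exclude that the web platform shows options in printed order. The first-option result depends on this. The 19.9%, and the fact that the correct number is always the lowest, do not.

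**Conclusion.** The point holds for the knowledge component. As printed, the key lets position alone reach the cut-off, and lets a lowest-number habit combined with guessing pass 62% of the time. Plain guessing passes 19.9% of the time. For informed choice the effect is smaller because attitude and intention must also agree.

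Type I error is not inflated. The likely direction is a scored difference somewhat too small, if the decision aid leaves fewer women uninformed than the brochure does: at most about one fifth of the true difference in adequate knowledge under the zero-knowledge, random-guessing assumption. How many women guess or follow the cue is unknown, so no figure for lost power can be given. The results rest on the inferred key and, for the first-option result, on display in printed order. This is a weakness worth removing before launch, not a fault that undermines the trial.

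**What to change.** Before launch, in both questionnaires and identically in both arms:

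1. Randomise or rotate the order of response options on the platform, and say so in Section 5.1.
2. Reset the distractors of the three numerical items so that the correct value is not always the lowest. Reordering alone does not achieve this.

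Keep the 13 items, the 8/13 threshold, the sample size and the chi-squared test. With fully random order, ticking the first option throughout becomes equivalent to guessing (mean 6.0, pass probability 19.9%). If the correct value is lowest in only one numerical item, the lowest-number habit needs seven of the other ten: 176/1024 = 17.2%, down from 62.3%. The 19.9% for pure guessing is unchanged.

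The cost is minor programming, a small change to Appendix 3 under the amendment procedure in Section 11.6, and slightly less comparability with the source instruments.

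An 'I don't know' answer scored 0 is optional and a trade-off. It would reduce guessing, but with 8/13 kept it makes the criterion stricter, and it may reflect confidence as well as knowledge.

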5.3 Translation of items

The items have been translated in Italian through a multistep process employing a standardized methodology. Briefly, one professional translator and two members of coordinating center (IRCCS Istituto Mario Negri) produced three independent Italian translations. After discussion, a common Italian version was produced. This version has been evaluated by partners (epidemiologists with experience in breast cancer screening, experts in communication, researchers of the project) in terms of use of simple, and correct language.

The preliminary Italian version of the questionnaires has been tested in a small group of women in order to evaluate clarity, understandability and length.

At the end of this process a final version has been established (Appendix 3).

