7. STUDY ASSESSMENTS

After registering in the web platform and signing the informed consent, participants must fill in a baseline questionnaire for participation in the study.

At baseline questionnaire, the following parameters will be evaluated:

- ✓ Demographics
- ✓ Use of internet
- ✓ Previous mammography test
- ✓ Previous participation at screening programmes
- ✓ Family history of breast cancer
- ✓ Perceived risk of breast cancer
- ✓ Knowledge on the breast cancer screening
- ✓ Attitude on the breast cancer screening
- ✓ Intention on the breast cancer screening

Baseline questionnaire will be performed prior to the randomization.

Follow-up questionnaire will be performed 7-10 days after randomization, before the appointment at the breast cancer screening.

At follow-up questionnaire, the following parameters will be evaluated:

- ✓ Knowledge on the breast cancer screening
- ✓ Attitude on the breast cancer screening
- ✓ Intention on the breast cancer screening
- ✓ Satisfaction and acceptability of the information received (web decision aid and web brochure)
- ✓ Decisional conflict

See Appendix 3 for both the baseline and the follow-up questionnaires.

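### Does the unprinted reverse-scoring key for the attitude items leave the primary endpoint undefined?

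*Combined protocol and SAP*

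**What the plan says.** Section 5.1 describes the attitude scale as "consisting of six items with five response options from 1 to 5, with a total score from 6 to 30" and then sets the cut: "we set the threshold for a positive attitude at 24 and consequently the score <24 point a negative attitude". It says that the scale has been used in two cited trials (references 22 and 27). The synopsis repeats the rule ("Attitude will be measured through a scale consisting of six items with five response options from 1 to 5"). A woman counts as having made an informed choice when her knowledge is adequate and her attitude and intention classes agree at follow-up.

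The items themselves appear only in Appendix 3, to which section 7 points: "See Appendix 3 for both the baseline and the follow-up questionnaires". Both questionnaires print the same six items, with the numbers 1 to 5 running from the left pole to the right. On the first item the right-hand pole, at 5, is "Not a bad thing", so 5 is favourable. On the second it is "Not beneficial", so 5 is unfavourable. Neither section 5.1 nor section 9.2 states which items are recoded.

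**The concern.** A literal reader could add the six printed numbers and compare the sum with 24. On these items that sum does not measure favourability, because four of the six run the opposite way to the other two. A woman strongly in favour of screening who intends to attend would then be attitude-negative and intention-positive. She would count as inconsistent, and so not informed, whatever her knowledge score. Since attitude enters the primary endpoint directly, a scoring error of this kind would reach the main result. A rule that needs a recode and does not mention one therefore deserves a check.

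**Working it through.** **Inputs.** Six items, codes 1 to 5, total 6 to 30, positive at 24 or more (section 5.1). Favourable pole at 5 for items 1 and 3, and at 1 for items 2, 4, 5 and 6 (Appendix 3, section 14.3).

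**The plan's own figures.** The range is 6 × 1 = 6 to 6 × 5 = 30. The cut-off of 24 equals 6 × 4, the total of a woman one step below the most favourable answer on every item. This reading makes sense only if 5 is favourable on every item after keying.

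**With reversal.** Score items 1 and 3 as printed and items 2, 4, 5 and 6 as 6 minus the response. The most favourable answers total 30, the least favourable 6, and the one-step-below pattern exactly 24. The rule in section 5.1 then works as worded.

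**Without reversal.** In item order:

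- most favourable: 5 + 1 + 5 + 1 + 1 + 1 = 14
- least favourable: 1 + 5 + 1 + 5 + 5 + 5 = 22

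Both fall below 24, and the order is inverted.

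**All patterns.** There are 5^6 = 15,625 response patterns. Those with a keyed total of 24 or more lose at most 6 points from 30, with at most 4 lost per item. Their number is C(12,6) − 6 × C(7,6) = 924 − 42 = 882.

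Let H be the keyed sum of items 1 and 3 (at most 10) and L the keyed sum of the other four items (at most 20). The keyed total is H + L. The printed total is H + (24 − L), since each of the four items prints as 6 minus its keyed value.

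- Keyed total of at least 24 requires L ≥ 24 − H ≥ 14.
- Printed total of at least 24 requires H ≥ L.
- With H ≤ 10 and L ≥ 14, both cannot hold.

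So 0 of the 882 reach 24 on the printed codes. Their printed totals run from 24 + 4 − 20 = 8 to 24 + 10 − 14 = 20.

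**How many keys fit.** Each item may be reversed or not: 2^6 = 64 keys. Every item keyed the wrong way takes 4 points off the most favourable total, so k wrong items give 30 − 4k. Only k = 0 gives 30, and that is one key of the 64. The mirror-image key, with all six items wrong, gives the most favourable woman 6 and is ruled out by calling a high total positive.

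**Sample size.** Section 9.1.3 compares 50% with 60% at 80% power and two-sided 5%. With the continuity correction this gives 408 per arm, or 816 in all, and 816 / (0.15 × 2/3) = 8160 invitations. Both figures reproduce, and item scoring enters neither.

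**The case for a change.** The best case for a change is that a rule for a primary endpoint should be executable from the protocol alone, and this one requires the programmer to infer the direction of four of the six items. Section 10.3 has one organisation hold the database and send a CSV file to another, without saying whether attitude answers are stored as printed or already keyed. A recode could therefore be omitted, or applied twice; either gives 14 and 22. A partial slip is less visible: with one reversal missed, the extreme records total 26 and 10 and are still classed correctly, yet only 280 of the 882 positive patterns stay at 24 or more (121 with two missed, 19 with three, 0 with four). It may also be said that section 5.1 gives an item rule for knowledge ("Each correct answer will receive one point") and none for attitude.

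What stands is that the key is not printed and that the arithmetic is right. The rest carries little weight. The partial-keying counts describe programming errors that the plan neither contains nor invites; they count possible patterns and are not misclassification rates. Catching such errors is ordinary program validation. The contrast with knowledge does not hold, because Appendix 3 marks no correct option for any knowledge question, so that key too is left to the content of the item. The cited trials may well give the attitude key; that cannot be checked from the documents, and the conclusion does not need it.

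**Conclusion.** No change to the plan follows. This is a gap that analysts fill sensibly: the item wording shows which pole is favourable, section 5.1 calls a high total positive, and one key of 64 satisfies both. No rival scoring competes with it, so the silence leaves no room to choose a score after seeing results. Writing the key down would record what any competent analyst would do, and would alter neither the cut-off, the test nor the sample size.

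The harm described, with 14 against 22 and both classed as negative, arises only if the printed codes are added unreversed or keyed codes are reversed again. The documents prescribe neither. No bias or loss of power can be derived from them.

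This rests on three assumptions: that the numbers printed in Appendix 3 reflect the fielded Italian items, that reversal is intended, and that item-level answers are kept, which the user-level records described in section 10.3 suggest. On the last assumption a scoring slip could be corrected without new data.
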